8.3.2. Neurological Examination

Neurological examinations may be conducted by a physician, trained physician's assistant, or nurse practitioner as acceptable according to local regulation at the nominal time points specified in the [SoA](#). The neurological exam will consist of assessment of higher cortical function, the cranial nerves, motor function, deep tendon reflexes, sensory exam, and coordination and gait. Additional neurological examinations that are outside of [SoA](#) (eg, to evaluate an AE) may be conducted at the discretion of investigator. All neurological exams should be done to the extent needed to assess the participant for any potential changes in neurological status, as determined by the investigator (or designee). Changes in the timing or addition of timepoints for the neurological examinations may occur based on emerging data.

8.3.3. Vital Signs

8.3.3.1. Blood Pressure and Pulse Rate

Supine BP will be measured with the participant's arm supported at the level of the heart, and recorded to the nearest mm Hg after approximately 5 minutes of rest. The same arm (preferably the dominant arm) will be used throughout the study. Participants should be instructed not to speak during measurements. When triplicate measurements of supine BP or pulse rate are required per [SoA](#), measurements should be collected 2-4 minutes apart.

The same properly sized and calibrated BP cuff will be used to measure BP each time. The use of an automated device for measuring BP and pulse rate is acceptable; however, when done manually, pulse rate will be measured in the brachial/radial artery for at least 30 seconds. When the timing of these measurements coincides with a blood collection, BP and pulse rate should be obtained prior to the nominal time of the blood collection.

Additional collection times, or changes to collection times, of BP and pulse rate will be permitted, as necessary, to ensure appropriate collection of safety data.

Any untoward vital sign findings that are identified during the active collection period and meet the definition of an AE or SAE ([Appendix 3](#)) must be reported according to the processes in [Sections 8.4.1 to 8.4.3](#).

8.3.3.2. Respiratory Rate

Respiratory rate will be measured after approximately 5 minutes of rest in a supine position by observing and counting the respirations of the participant for 30 seconds and multiplying by 2. When BP is to be taken at the same time, respiration measurement will be done during the 5 minutes of rest and before BP measurement.

8.3.3.3. Temperature

Temperature will be measured orally. No eating, drinking, or smoking is allowed for 15 minutes prior to the measurement.

8.3.4. Electrocardiograms

Standard 12-lead ECGs will be collected at times specified in the [SoA](#) section of this protocol using an ECG system that automatically calculates the HR and measures PR, QT, QTcF, and QRS intervals. All scheduled ECGs should be performed after the participant has rested quietly for at least 5 minutes in a supine position.

Triplet 12-lead ECGs (as specified in the [SoA](#)) will be obtained approximately 2 to 4 minutes apart; the average of the triplicate ECG measurements collected at -1.0, -0.5, and 0 hours pre-dose on Day 1 of each period will serve as each participant's baseline QTcF value for that period.

To ensure safety of the participants, a qualified individual at the investigator site will make comparisons to baseline measurements. Additional ECG monitoring will occur if a) the mean value from the triplicate measurements for any post-dose QTcF interval is increased by ≥ 60 ms from the baseline and is >450 ms; or b) an absolute QT value is ≥ 500 ms for any scheduled ECG. If either of these conditions occurs, then a single ECG measurement must be repeated at least hourly until QTcF values from 2 successive ECGs fall below the threshold value that triggered the repeat measurement.

For single ECG collections, additional ECG monitoring will occur if a) a postdose QTcF interval is increased by ≥ 60 ms from the baseline and is >450 ms; or b) an absolute QT value is ≥ 500 ms for any scheduled ECG. If either of these conditions occurs, then 2 additional

ECGs will be collected approximately 2 -4 minutes apart to confirm the original measurement. If the QTcF values from these repeated ECGs remain above the threshold value, then a single ECG must be repeated at least hourly until QTc values from 2 successive ECGs fall below the threshold value that triggered the repeat measurement.

If a) a post-dose QTcF interval remains ≥ 60 ms from the baseline and is >450 ms; or b) an absolute QT value is ≥ 500 ms for any scheduled ECG for greater than 4 hours (or sooner, at the discretion of the investigator); or c) QTcF value get progressively longer, the participant should undergo continuous ECG monitoring. A cardiologist should be consulted if QTcF values do not return to less than the criteria listed above after 8 hours of monitoring (or sooner, at the discretion of the investigator).

In some cases, it may be appropriate to repeat abnormal ECGs to rule out improper lead placement as contributing to the ECG abnormality. It is important that leads be placed in the same positions each time in order to achieve precise ECG recordings. If a machine-read QTc value is prolonged, as defined above, repeat measurements may not be necessary if a qualified medical provider's interpretation determines that the QTcF values are in the acceptable range.

ECG values of potential clinical concern are listed in [Appendix 8](#).

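### Protocol 8.3.4 starts repeat ECGs on an absolute QT of 500 ms or more but confirms, ends and refers on QTcF, and the two agree only at 60 bpm

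*Protocol*

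**What the plan says.** Protocol 8.3.4 says that the ECG system "measures PR, QT, QTcF, and QRS intervals", so QT and QTcF are distinct recorded values.

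Additional ECGs are triggered by either of two arms. Arm (a) is a post-dose QTcF rise of at least 60 ms to a value above 450 ms. Arm (b) is an absolute QT of at least 500 ms: "from the baseline and is >450 ms; or b) an absolute QT value is" at least that figure. The pair appears three times: for triplicate ECGs, for single ECGs, and in the test for findings that persist beyond 4 hours, which leads to continuous ECG monitoring. That test adds a condition (c), progressive QTcF lengthening.

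The steps that follow a trigger name a different interval from arm (b):

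- After a triplicate, "a single ECG measurement must be repeated at least hourly until QTcF values from 2 successive ECGs fall below the threshold value that triggered" them.
- After a single ECG, two more are taken. "If the QTcF values from these repeated ECGs remain above the threshold value", hourly repeats begin and continue "until QTc values from 2 successive ECGs fall below the threshold value that triggered the repeat measurement".
- "A cardiologist should be consulted if QTcF values do not return to less than the criteria listed above after 8 hours of monitoring"; the investigator may bring this forward.
- "If a machine-read QTc value is prolonged, as defined above, repeat measurements may not be necessary", provided that a qualified medical provider judges the QTcF values acceptable.

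Protocol 7.1.2 separately withdraws a participant from study intervention when the triplicate-average QTcF exceeds 500 ms or has risen by more than 60 ms.

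**The concern.** The confirmation and end rules refer back to the threshold that started the repeats. Under arm (a) that threshold is on QTcF, and the chain is coherent. Under arm (b) it is on QT as written, so a QTcF is compared with a QT limit. The two scales differ at every heart rate except 60 bpm, so two staff members who both follow the text could act differently on the same tracing.

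These are mandatory instructions carried out by site staff in a first-in-human study whose primary endpoint includes 12-lead ECGs. What is at stake is whether repeat ECGs start, when they stop and whether the referral step is reached. No sample size, error rate or planned summary is involved.

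**Working it through.** The plan gives no figure to reproduce here. The check has two parts: which interval each step names, and how far apart the intervals lie.

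**Interval named at each step of 8.3.4**

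| Step | Interval |
|---|---|
| Trigger (a), triplicate and single | QTcF |
| Trigger (b), triplicate and single | absolute QT, at least 500 ms |
| Confirmation (single ECGs only) | QTcF |
| End of repeats after a triplicate | QTcF |
| End of repeats after a single ECG | QTc |
| Test beyond 4 hours, arm (a) | QTcF |
| Test beyond 4 hours, arm (b) | absolute QT, at least 500 ms |
| Test beyond 4 hours, condition (c) | QTcF |
| Cardiologist referral | QTcF |

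**Size of the gap**

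Formula (SAP 3.1.5): QTcF = QT / RR^(1/3), with RR = 60/HR in seconds. The heart rates below are illustrative assumptions. At 50 bpm, for example, RR = 1.2 and 500 / 1.2^(1/3) = 470.5.

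| HR (bpm) | QTcF when QT = 500 ms | QT when QTcF = 500 ms |
|---|---|---|
| 45 | 454.3 | 550.3 |
| 50 | 470.5 | 531.3 |
| 55 | 485.7 | 514.7 |
| 60 | 500.0 | 500.0 |
| 70 | 526.4 | 475.0 |
| 80 | 550.3 | 454.3 |

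**Reading 1: arm (b) means uncorrected QT**

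*Below 60 bpm.* Take QT 501 ms at 45 bpm. QTcF = 501 / (60/45)^(1/3) = 455.2 ms. Arm (a) then needs a baseline of 455.2 − 60 = 395.2 ms or lower; with a higher baseline only (b) is met. If nothing changes, two successive repeats each show QTcF 455 ms, below 500, and the end rule is satisfied with QT still 501 ms. On the single-ECG path the two confirmatory tracings also show QTcF 455 ms, so hourly repeats do not begin. On (b) alone this holds while QTcF stays below 500 ms, that is, for QT below about 515 ms at 55 bpm, 531 at 50 and 550 at 45. Referral judged on QTcF has the same limit.

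*Above 60 bpm.* QTcF can be 500 ms or more while QT is lower, so (b) is not met. Assume a baseline QTcF of 445 ms (protocol 5.2 gives a screening QTcF above 450 ms as an example of an excluding abnormality) and a post-dose triplicate-mean QTcF of 502 ms at 70 bpm:

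- QT = 502 × (60/70)^(1/3) = 476.9 ms, below 500, so (b) is not met.
- The rise is 502 − 445 = 57 ms, below 60, so (a) is not met.
- The first withdrawal criterion in 7.1.2, triplicate-average QTcF above 500 ms, is met.

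So 8.3.4 requires no repeat ECG for a value that leads to withdrawal of study intervention under 7.1.2.

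**Reading 2: arm (b) means QTcF**

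The heart-rate problem disappears and the steps line up, but the interval is misnamed in both triggers and in the test beyond 4 hours. The section does not say that this is what is meant.

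**The case against.** The strongest reply is that 8.3.4 is coherent under either reading. If raw QT is meant, it can be seen as a sensitive alert that is then adjudicated on QTcF; the closing paragraph supports this by letting a provider's view of QTcF decide whether repeats are needed. If QTcF is meant, the fault is two missing letters. Other sections do not settle the matter. Protocol 9.3.1.1 writes uncorrected QT where it means that, and Appendix 8 uses the word absolute for QTcF; both favour the second reading. But 9.3.1.1 also tabulates uncorrected QT above 500 ms, which suggests that the raw figure may be deliberate.

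Much of this stands as to impact. It does not remove the mismatch: the end rules point back to the triggering threshold, not to a separate QTcF criterion, and an alert on raw QT would still miss a QTcF above 500 ms at faster heart rates.

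A reader might infer more than the documents support:

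- *That QTc is a third interval.* Fridericia is the only correction named in either document, so QTc can only be QTcF.
- *That slow heart rates from 40 to 60 bpm escape notice.* Appendix 8 also lists symptomatic bradycardia, with no rate limit.
- *That the 450 ms floor in arm (a) contradicts the rise criterion in 7.1.2, which has none.* The two rules serve different purposes and can both be obeyed. Appendix 8 itself separates a rise above 60 ms alone from the same rise with QTcF above 450 ms.
- *That a participant with long QT is left unmonitored or never referred.* The effects shown hold only on (b) alone and only while QTcF is below 500 ms. Arm (b) of the test beyond 4 hours stays on QT throughout.

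**Conclusion.** The inconsistency is real and should be corrected before the section is relied on. Arm (b) names QT in all three places, while confirmation, ending and referral use QTcF. Followed literally, the rules can stop repeats with QT still at 500 ms or more below 60 bpm, and can omit repeats with QTcF at 500 ms or more above it. The gap is 14 ms at 55 bpm (500 − 486) and 46 ms at 45 bpm (500 − 454); at 70 bpm it is 25 ms in the other direction (500 − 475). If QTcF was intended, the fault is one misnamed interval, three times.

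The practical impact is limited. Telemetry for 8 hours after dosing, condition (c), investigator discretion and later scheduled ECGs all remain. Post-dose single ECGs occur only at the follow-up visit and early termination, so the confirmation problem is confined to those visits. The planned QTcF analyses are unaffected.

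The size rests on the SAP's Fridericia formula and on assumed heart rates and QTcF values. The documents give no distribution of heart rate or baseline QTcF, so how often either situation would arise cannot be estimated.

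**What to change.** Reconcile 8.3.4 so that one named interval runs through the trigger, single-ECG confirmation, end of repeats, test beyond 4 hours and cardiologist referral, and write QTcF in place of QTc where that is meant. If different intervals at different steps are intended, say so and state the threshold for each step. Then check the result against the QTcF withdrawal criteria in 7.1.2, so that a value meeting one section is not passed over by the other without explanation. Which interval and threshold to use is for the sponsor to decide.

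The cost is protocol wording only. No new assessment, sample or analysis is needed.

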8.3.4.1. Continuous Cardiac Monitoring by Telemetry

All abnormal rhythms will be recorded and reviewed by the study physician for the presence of rhythms of potential clinical concern. The time, duration, and description of the clinically significant event will be recorded in the CRF. In addition, a printed record of the tracing(s) of the clinically significant rhythm(s) will be made and retained with other source documents.

Telemetry should be collected using a centralized system that also allows for the storage and advanced analysis of all recorded data in order to preserve important events for future evaluations. Holter monitoring should not be used in parallel with continuous telemetry, unless it is the only means of data storage available at the investigator site, or verifiable arrhythmia quantification is required. To establish a baseline, telemetry should be recorded for at least 2 hours before dosing in Period 1. This may be done immediately prior to dosing or at some 2-hour continuous interval in the 24 hours prior to dosing, as long as the recording is performed when the participant is awake. Post-dose telemetry will continue for 8 hours after dosing. Telemetry may be stopped within a reasonably short period of time prior to dosing, in order to avoid interference with study operations conducted immediately before dosing. However, it is expected that the telemetry leads will be in place and the system connected prior to dosing.

8.3.5. Clinical Safety Laboratory Assessments

See [Appendix 2](#) for the list of clinical safety laboratory tests to be performed and the [SoA](#) for the timing and frequency. All protocol required laboratory assessments, as defined in [Appendix 2](#), must be conducted in accordance with the laboratory manual and the [SoA](#). Unscheduled clinical laboratory measurements may be obtained at any time during the study to assess any perceived safety issues.

The investigator must review the laboratory report, document this review, and record any clinically significant changes occurring during the study in the AE section of the CRF. Clinically significant abnormal laboratory test findings are those that are not associated with the underlying disease, unless judged by the investigator to be more severe than expected for the participant's condition.

All laboratory tests with values considered clinically significant and abnormal during participation in the study or within 28 days after the last dose of study intervention should be repeated until the values return to normal or baseline or are no longer considered clinically significant by the investigator or study medical monitor.

If such values do not return to normal/baseline within a period of time judged reasonable by the investigator, the etiology should be identified and the sponsor notified.

See [Appendix 6](#) for suggested actions and follow-up assessments in the event of potential DILI.

See [Appendix 7](#) for instructions for laboratory testing to monitor kidney function and reporting laboratory test abnormalities.

Participants may undergo random urine drug testing at the discretion of the investigator. Drug testing conducted prior to dosing must be negative for participants to receive study intervention.

8.3.6. COVID-19 Specific Assessments

Participants will be tested for COVID-19 infection per CRU procedures.

8.4. Adverse Events, Serious Adverse Events, and Other Safety Reporting

The definitions of an AE and an SAE can be found in [Appendix 3](#).

AEs may arise from symptoms or other complaints reported to the investigator by the participant (or, when appropriate, by a caregiver, surrogate, or the participant's legally authorized representative), or they may arise from clinical findings of the investigator or other healthcare providers (clinical signs, test results, etc).

The investigator and any qualified designees are responsible for detecting, documenting, and recording events that meet the definition of an AE or SAE and remain responsible to pursue and obtain adequate information both to determine the outcome and to assess whether the event meets the criteria for classification as an SAE or caused the participant to discontinue the study (see [Section 7.1](#)).

During the active collection period as described in [Section 8.4.1](#), each participant will be questioned about the occurrence of AEs in a nonleading manner.

In addition, the investigator may be requested by Pfizer Safety to obtain specific follow-up information in an expedited fashion.

8.4.1. Time Period and Frequency for Collecting AE and SAE Information

The time period for actively eliciting and collecting AEs and SAEs (“active collection period”) for each participant begins from the time the participant provides informed consent, which is obtained before undergoing any study-related procedure and/or receiving study intervention), through and including a minimum of 28 calendar days, except as indicated below, after the last administration of the study intervention.

Follow-up by the investigator continues throughout the active collection period and until the AE or SAE or its sequelae resolve or stabilize at a level acceptable to the investigator.

When a clinically important AE remains ongoing at the end of the active collection period, follow-up by the investigator continues until the AE or SAE or its sequelae resolve or stabilize at a level acceptable to the investigator and Pfizer concurs with that assessment.

For participants who are screen failures, the active collection period ends when screen failure status is determined.

If the participant withdraws from the study and also withdraws consent for the collection of future information, the active collection period ends when consent is withdrawn.

If a participant permanently discontinues or temporarily discontinues study intervention because of an AE or SAE, the AE or SAE must be recorded on the CRF and the SAE reported using the CT SAE Report Form.

Investigators are not obligated to actively seek information on AEs or SAEs after the participant has concluded study participation. However, if the investigator learns of any SAE, including a death, at any time after a participant has concluded study participation, and they consider the event to be reasonably related to the study intervention, the investigator must promptly report the SAE to Pfizer using the CT SAE Report Form/ PSSA.

8.4.1.1. Reporting SAEs to Pfizer Safety

All SAEs occurring in a participant during the active collection period as described in [Section 8.4.1](#) are reported to Pfizer Safety on the CT SAE Report Form/PSSA immediately upon awareness and under no circumstance should this exceed 24 hours, as indicated in [Appendix 3](#). The investigator will submit any updated SAE data to the sponsor within 24 hours of its being available.

8.4.1.2. Recording Nonserious AEs and SAEs on the CRF

All nonserious AEs and SAEs occurring in a participant during the active collection period, which begins after obtaining informed consent as described in [Section 8.4.1](#), will be recorded on the AE section of the CRF.

The investigator is to record on the CRF all directly observed and all spontaneously reported AEs and SAEs reported by the participant.

As part of ongoing safety reviews conducted by the sponsor, any nonserious AE that is determined by the sponsor to be serious will be reported by the sponsor as an SAE. To assist in the determination of case seriousness, further information may be requested from the investigator to provide clarity and understanding of the event in the context of the clinical study.

Reporting of AEs and SAEs for participants who fail screening are subject to the CRF requirements as described in [Section 5.4](#).

8.4.2. Method of Detecting AEs and SAEs

The method of recording, evaluating, and assessing causality of AEs and SAEs and the procedures for completing and transmitting SAE reports are provided in [Appendix 3](#).

Care will be taken not to introduce bias when detecting AEs and/or SAEs. Open-ended and nonleading verbal questioning of the participant is the preferred method to inquire about AE occurrences.

8.4.3. Follow-Up of AEs and SAEs

After the initial AE or SAE report, the investigator is required to proactively follow each participant at subsequent visits/contacts. For each event, the investigator must pursue and obtain adequate information until resolution, stabilization, the event is otherwise explained, or the participant is lost to follow-up (as defined in [Section 7.3](#)).

In general, follow-up information will include a description of the event in sufficient detail to allow for a complete medical assessment of the case and independent determination of possible causality. Any information relevant to the event, such as concomitant medications and illnesses, must be provided. In the case of a participant death, a summary of available autopsy findings must be submitted as soon as possible to Pfizer Safety.

Further information on follow-up procedures is provided in [Appendix 3](#).

8.4.4. Regulatory Reporting Requirements for SAEs

Prompt notification by the investigator to the sponsor of an SAE is essential so that legal obligations and ethical responsibilities toward the safety of participants and the safety of a study intervention under clinical investigation are met.

The sponsor has a legal responsibility to notify both the local regulatory authority and other regulatory agencies about the safety of a study intervention under clinical investigation. The sponsor will comply with country -specific regulatory requirements relating to safety reporting to the regulatory authority, IRBs/ECs, and investigators.

Investigator safety reports must be prepared for SUSARs according to local regulatory requirements and sponsor policy and forwarded to investigators as necessary.

An investigator who receives SUSARs or other specific safety information (eg, summary or listing of SAEs) from the sponsor will review and then file it along with the SRSD(s) for the study and will notify the IRB/EC, if appropriate according to local requirements.

8.4.5. Environmental Exposure, Exposure During Pregnancy or Breastfeeding, and Occupational Exposure

Environmental exposure, occurs when a person not enrolled in the study as a participant receives unplanned direct contact with or exposure to the study intervention. Such exposure may or may not lead to the occurrence of an AE or SAE. Persons at risk for environmental exposure include healthcare providers, family members, and others who may be exposed. An environmental exposure may include EDP, EDB, and occupational exposure.

Any such exposures to the study intervention under study are reportable to Pfizer Safety within 24 hours of investigator awareness.

